#### **10.4.2 Identity of Investigational Products**

Investigational materials will be provided by the Sponsor as in [Table 2](#).

**Table 2: Product Descriptions**

Product	Description
Test	E-WE thrombin (0.1 mg/mL)
Placebo	Placebo for E-WE thrombin (16.2 mM sodium citrate, 3.8 mM citric acid, 150 mM sodium chloride, 0.1% polysorbate 80, at pH 6)

#### **10.4.3 Method of Assigning Subjects to Treatment Groups**

Each subject will be assigned a unique identification number upon screening. Subjects who complete the study screening assessments and meet all the eligibility criteria will be assigned a unique randomization identification number prior to the dosing, different from the screening number, and will receive the corresponding product according to a randomization scheme generated at Celerion.

In Cohort 1, the sentinel group will consist of 2 subjects who will be randomized to receive E-WE thrombin or placebo (1 active and 1 placebo). The remaining 4 subjects in the cohort will be randomized to receive E-WE thrombin or placebo (3 active and 1 placebo).

In Cohorts 2-4, subjects will be randomized to receive a single IV bolus of E-WE thrombin or placebo in a 4:1. Subjects will participate in only one cohort.

The remaining subjects in Cohort 1 (non-sentinel subjects) will be dosed at least 28 days after the Cohort 1 sentinel group. The remaining subjects in Cohort 1 and subjects in Cohorts 2, 3, and 4 will be dosed in 2 groups separated by at least 14 days (2 subjects in each group [Cohort 1] or 2 subjects in the first group and 3 subjects in the second group [Cohorts 2-4]). The placebo will be randomized to either group.

Subjects in the first enrollment cohort will be numbered 1001 – 1006; subjects in the second enrollment cohort will be numbered 2001 - 2005, etc.

If replacement subjects are used, the replacement subject number will be 100 more than the original (e.g., Subject No. 1101 will replace Subject No. 1001).

#### **10.4.4 Blinding**

This is a double-blind, placebo-controlled study.

##### **10.4.4.1 Maintenance of Randomization**

A computerized randomization scheme will be created by a Celerion statistician and it shall be considered blinded as per the following: the randomization is available only to the clinic pharmacy staff preparing the drug who will not be involved in any other aspect of the study including administration of the drug. It will not be made available to the Sponsor,

bioanalytical laboratory, subjects, or members of the staff responsible for the monitoring and evaluation of safety assessments.

#### **10.4.4.2 Procedures for Breaking the Blind Prior to Study Completion**

One set of sealed envelopes containing the randomization code will be supplied to the PI or designee at the start of the study.

Breaking of the blind is expressly forbidden except in the event of a medical emergency (e.g., SAEs and other AEs  $\geq$  grade 3 that are considered possibly related to the study treatment) where the identity of the drug must be known in order to properly treat the subject, or in the event of a safety interim analysis at the request of the Sponsor.

In the event of a medical emergency, it is requested that the PI or designee make every effort to contact the Study Monitor or designee prior to breaking the blind. If breaking the blind is required because of a medical emergency, the treatment identity would be revealed by the PI or designee, for that subject only. In the event that the emergency is one, in which it appears that the other subjects may be at imminent risk, the blind may be broken for all subjects dosed at that dose level. The unblinding will be properly documented in the study file.

In all cases where the code is broken, the PI or designee should record the date and reason for code breaking.

At the end of the study, envelopes will be retained or destroyed according to site procedures unless specified otherwise by the Sponsor.

#### **10.4.4.3 Interim Analysis**

##### Safety:

If there are safety concerns, all available blinded safety data will be reviewed by the SRC prior to dose escalation.

At the Sponsor's request, unblinded safety tables, figures, and data listings may be presented to the sponsor's medical expert and head of regulatory for the purposes of planning the next initial Phase 2 studies prior to database lock. These interim analyses will be performed on data that will be edit-checked and monitored.

A safety programmer and a biostatistician at Celerion who are not involved with the present study will be unblinded to prepare the required unblinded safety tables, figures, and data listings. All the personnel related to the present study will remain blinded.

#### **10.4.4.4 Revealing of Randomization**

In the absence of a medical emergency, the blinded randomization for this study will not be revealed until all data are entered in the database, edits checks are performed, queries closed, case report forms (CRFs) signed by the PI, and the database is officially locked.

#### **10.4.5 Treatment Compliance**

A qualified designee will be responsible for administering and monitoring the timed dose. Before and after IV bolus injection, the qualified designee will visually inspect the syringe to ensure that the subject has received the entire dose. In the case of an incomplete dosing (e.g., large droplet of study medication on the surface of the skin) as deemed by the PI (or designee) and/or Sponsor, the subject may be withdrawn. Subjects withdrawn for incomplete dosing will be asked to remain at the CRU after drug administration and be monitored through Day 28 or 7 days ( $\pm 2$  days) after aPTT and thrombin time values have returned within  $\pm 10\%$  of the baseline value or the normal range (whichever occurs later), similarly to other study participants.

## **11. STUDY PROCEDURES**

### **11.1 Safety Assessments**

The Study Events Flow Chart ([Section 6](#)) summarizes the clinical procedures to be performed at each visit. Individual clinical procedures are described in detail below. Additional evaluations/testing may be deemed necessary by the PI or designee and/or the Sponsor for reasons related to subject safety.

For this study, the primary assessment is the safety and tolerability. Safety will be determined by evaluating vital signs, ECGs, clinical laboratory parameters, including but not limited to, hematology, clinical chemistry profile, coagulation, and urinalysis, immunogenicity, injection site reaction, and AEs as outlined in the Study Events Flow Chart ([Section 6](#)).

Any nonscheduled procedures required for urgent evaluation of safety concerns take precedence over all routine scheduled procedures.

#### **11.1.1 Body Height and Weight**

Body height (cm) and body weight (kg) will be measured as outlined in the Study Events Flow Chart ([Section 6](#)). BMI will be calculated at screening.

#### **11.1.2 Physical Examination and Medical History**

A full physical examination will be performed as per Study Events Flow Chart ([Section 6](#)) and will include, at a minimum, assessment of the following systems: skin, head, ears, eyes, nose and throat, respiratory system, cardiovascular system, gastrointestinal system, neurological condition, blood and lymphatic systems, and the musculoskeletal system.

Symptom-driven physical examination may be performed at other times, if deemed necessary by the PI or designee.

#### **11.1.3 Vital Signs**

Single measurements of body temperature, respiratory rate, blood pressure, and heart rate, will be measured as outlined in the Study Events Flow Chart ([Section 6](#)). Additional vital signs may be taken at any other times, if deemed necessary.

Vital sign measurements will be performed with subjects in a supine position, except when they are standing or semi-reclined because of study procedures and/or AEs (e.g., nausea, dizziness) or if deemed necessary by the PI or designee.

Vital signs will be measured within 24 hours prior to dosing for the predose time point. When scheduled postdose, vital signs will be performed within approximately 10 minutes of the scheduled time point.

### **11.1.3.1 Safety 12-Lead ECGs**

Single 12-lead ECGs will be performed as outlined in the Study Events Flow Chart ([Section 6](#)). Additional ECGs may be taken at any other times, if deemed necessary by the PI or designee.

ECGs will be taken following resting in the supine position. All ECG tracings will be reviewed by the PI or designee.

ECGs will be measured within 24 hours prior to dosing for the predose time point. When scheduled postdose, ECGs will be performed within approximately 20 minutes of the scheduled time point.

#### 11.1.4 Clinical Laboratory Tests

All tests listed below will be performed as per Study Events Flow Chart ([Section 6](#)). In addition, laboratory safety tests may be performed at various unscheduled time points, if deemed necessary by the PI or designee.

##### Hematology

- Hemoglobin
- Hematocrit
- Total and differential leukocyte count
- Red blood cell count
- Platelet count

##### Coagulation

- PT/INR
- aPTT
- Fibrinogen
- Thrombin time

##### Urinalysis

- pH
- Specific gravity
- Protein\*\*\*
- Glucose
- Ketones
- Bilirubin
- Blood\*\*\*
- Nitrite\*\*\*
- Urobilinogen
- Leukocyte esterase\*\*\*

##### Serum Chemistry\*

- Blood Urea Nitrogen
- Bilirubin (total and direct)
- Alkaline phosphatase
- Aspartate aminotransferase
- Alanine aminotransferase
- Lactate dehydrogenase
- Albumin
- Sodium
- Potassium
- Bicarbonate
- Chloride
- Glucose (fasting)
- Creatinine\*\*

##### Additional Tests

- HIV test
- HBsAg
- HCV
- Urine drug screen
  - Opiates
  - Amphetamines
  - Cocaine
  - Cannabinoids
- Urine alcohol screen
- Serum pregnancy test (for females only)
- FSH (for postmenopausal females only)

\* Serum chemistry tests will be performed after at least an 8-hour fast; however, in case of dropouts or rechecks, subjects may not have fasted for 8 hours before the serum chemistry sample is taken.

\*\* At screening, creatinine clearance will be calculated using the Cockcroft-Gault formula.

\*\*\* If urinalysis is positive for protein, blood, nitrite and/or leukocyte esterase, a microscopic examination (for red blood cells, white blood cells, bacteria, casts, and epithelial cells) will be performed.

#### 11.1.5 Check-In Questionnaire

A check-in questionnaire will be reviewed for each subject to ensure that they remain eligible for the study. The questions will be based on the inclusion and exclusion criteria and study restrictions.

### 11.1.6 Injection Site Reaction Assessment

The monitoring of AEs will pay special attention to potential injection site reactions. Therefore, at specified time points, inspection of administration and surrounding area will be performed. Any abnormal findings will be reported as AEs. Injection and needle puncture site reactions for drug administration will be evaluated as outlined in the Study Events Flow Chart (Section 6). Prior to dosing, the injection site will be examined. When scheduled postdose, injection site examinations will be performed within approximately 20 minutes of the scheduled time point. Reactions will be rated according to the FDA Guidance for Industry: Toxicity Grading Scale for Healthy Adult and Adolescent Volunteers Enrolled in Preventative Vaccine Clinical Trials (Sep 2007), [6] as follows:

Local Reaction	Mild (Grade 1)	Moderate (Grade 2)	Severe (Grade 3)
Pain	Does not interfere with activity	Repeated use of non-narcotic pain reliever > 24 hours or interferes with activity	Any use of narcotic pain reliever or prevents daily activity
Tenderness	Mild discomfort to touch	Discomfort with movement	Significant discomfort at rest
Erythema/Redness*	2.5 – 5 cm	5.1 – 10 cm	> 10 cm
Induration/Swelling**	2.5 – 5 cm and does not interfere with activity	5.1 – 10 cm or interferes with activity	> 10 cm or prevents daily activity

\* In addition to grading the measured local reaction at the greatest single diameter, the measurement should be recorded as a continuous variable.

\*\* Induration/swelling should be evaluated and graded using the functional scale as well as the actual measurement.

### 11.1.7 Immunogenicity

Blood samples for immunogenicity assessment will be performed as per Study Events Flow Chart (Section 6).

#### 11.1.7.1 Blood Sampling and Processing for Immunogenicity

Blood samples for immunogenicity assessment (i.e., E-WE thrombin and wild type [WT] thrombin) will be performed as per Study Events Flow Chart (Section 6).

For the determination of E-WE thrombin ADA, blood samples will be collected in 2 blood collection tubes of 4.5 mL each, containing 3.2% sodium citrate, and processed into three plasma aliquots of at least 0.5 mL each.

For the determination of WT thrombin ADA, whole blood samples will be collected in a 5 mL blood collection tube, without anticoagulant, and processed to 3 serum aliquots of 0.5 mL each.

Samples will be shipped to the analytical laboratory for analysis at the end of the study, unless ADA or cross reacting antibodies are suspected from thrombin time elevation at Day 14 or Day 28.

Instruction for blood sampling, collection, processing, and sample shipment will be provided separately.

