	
Blood samples will be collected for PD assessment (i.e., APC-PCI) of E-WE thrombin at scheduled time points listed in the Study Events Flow Chart (Section 6) predose and for 24 hours postdose.
 
Dose escalation to the next dose level (i.e., next cohort) will not take place until after the Principal Investigator (PI) has reviewed the safety data and informed the Sponsor of the findings. If any findings in the safety data are of concern, then the Safety Review Committee (SRC) comprised of but not limited to, the Sponsor, medical monitor, and the PI will convene to determine if adequate safety and tolerability from the previous cohorts, including activated partial thromboplastin time (aPTT), has been demonstrated to permit proceeding to the next cohort.
 
For each cohort, 14 days of safety data will be used and reviewed for a dose escalation decision. Data from all subjects in the appropriate cohort will be used and reviewed for a dose escalation decision. aPTT and thrombin time should be in the normal range (unless it is still within <math>\pm 10\%</math> of individual's baseline value taken at check-in) at Day 14 to rule out early cross-reacting antibodies to thrombin/prothrombin. A minimum of 4 subjects in each cohort must complete the study (up to Day 14) before proceeding to the next higher dosing cohort.
 
Subjects dosed on the same day will be dosed with an interval of at least 1 hour between subjects.
 
Subjects (including those who terminate early) will return on Days 14 and 28 for follow-up procedures (coagulation sample collection, thrombin time measurement, and immunogenicity sample collection) and to determine if any AE has occurred since the last study visit. If thrombin time and/or aPTT are found to be elevated beyond normal range (unless it is still within <math>\pm 10\%</math> of individual's baseline value at check-in) at Day 14, both tests will be repeated. If aPTT and/or thrombin time are elevated beyond normal range in the retest, a mixing study will be performed. The mixing study will be performed on Day 14 by mixing the subjects' plasma 1:1 with normal human pooled plasma. aPTT and thrombin time will be evaluated. If the aPTT and/or thrombin time does not correct to normal range, the presence of anti-drug antibodies (ADA) and cross-reacting prothrombin/thrombin antibodies will be presumed, and will be directly assessed before dose escalation decision.
 
Subjects who terminate the study early will be asked to continue aPTT and thrombin time monitoring as scheduled until Day 28.
 
Any subjects for whom aPTT and/or thrombin time did not reach

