- j If thrombin time and/or aPTT are found to be elevated at Day 14, both tests will be repeated. If aPTT and/or thrombin time are elevated beyond the normal range (unless it is still within  $\pm 10\%$  of individual's baseline value at check-in) in the retest, a mixing study will be performed. The mixing study will be performed on Day 14 by mixing the subjects' plasma 1:1 with normal human pooled plasma. aPTT and thrombin time will be evaluated. If the aPTT and/or thrombin time do not correct to normal range, the presence of ADA cross-reacting prothrombin/thrombin antibodies will be presumed. The applicable subject will remain at the CRU until

these test results are obtained. Subjects for whom aPTT and/or thrombin time did not reach  $\pm 10\%$  of the baseline value or within the normal range by Day 14, will return every 7 days ( $\pm 2$  days) until aPTT and thrombin time reach  $\pm 10\%$  of the baseline value or within the normal range.

- k Subjects in the sentinel group (Cohort 1 only) will be dosed at least 28 days prior to remaining subjects. The remaining subjects in Cohort 1 and subjects in the Cohorts 2, 3, and 4 will be dosed in two groups separated by at least 14 days. Dosing in each group will be staggered by at least 1 hour.
- l: Immunogenicity testing for ADA will be first performed on blood samples taken on Days 14 and 28. If ADA are found, the check-in sample of ADA will be evaluated.

Abbreviations: ADA = Anti-drug antibodies, AE = Adverse event, APC-PCI = Activated protein C with protein C inhibitor, aPTT = Activated partial thromboplastin time, C-I = Check-in, Chem = Chemistry, CRU = Clinical research unit, FSH = Follicle-stimulating hormone, FU = Follow-up, Hem = Hematology, HIV = Human immunodeficiency virus, INR = International normalized ratio, PD = Pharmacodynamic, PI = Principal Investigator, PT = Prothrombin time, Scr = Screening, UA = Urinalysis.

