#### **10.4.1.2 Planned Dose Levels**

The planned dose levels are as follows:

Cohort 1: 0.5 mcg/kg E-WE thrombin or matching placebo (IV bolus)

Cohort 2: 1.0 mcg/kg E-WE thrombin or matching placebo (IV bolus)

Cohort 3: 2.0 mcg/kg E-WE thrombin or matching placebo (IV bolus)

Cohort 4: 4.0 mcg/kg E-WE thrombin or matching placebo (IV bolus)

Note: The planned dose levels described above may be revised up or down or a dose level may be repeated based upon data from a previous dose level, however, doses will not exceed 4.0 mcg/kg without a protocol amendment.

For Cohort 1 there will be a sentinel group comprised of 2 subjects dosed at least 28 days before the remaining group of subjects; subjects will be randomized in a 1:1 ratio to active and placebo. The remaining subjects in the cohort will be dosed after evaluation of the sentinel subjects' Day 28 safety data and will be dosed in 2 groups separated by at least 14 days (2 subjects in the first group and 2 subjects in the second group). The placebo will be randomized to either group.

The Cohorts 2, 3, and 4 will be dosed in 2 groups separated by at least 14 days (2 subjects in the first group and 3 subjects in the second group). The placebo will be randomized to either group.

Thrombin time and aPTT at Day 14 will be tested to evaluate whether or not subjects may be generating neutralizing antibodies to thrombin/prothrombin. If the thrombin time and aPTTs are normal, the next cohort may be dosed if the rest of the safety data is deemed acceptable by the PI or SRC, as applicable. Confirmation of safety data from the previous cohorts will include for Cohort 1, 6 subjects (4 active and 2 placebo) and for Cohorts 2, 3, and 4, 5 subjects (4 active and 1 placebo).

If thrombin time and/or aPTT are found to be elevated beyond normal range (unless it is still within  $\pm 10\%$  of individual's baseline value at check-in) at Day 14, both tests will be repeated. If aPTT and/or thrombin time are elevated beyond normal range in the retest, a mixing study will be performed. The mixing study will be performed by mixing the subjects' plasma 1:1 with normal human pooled plasma. aPTT and thrombin time will be evaluated. If the aPTT and/or thrombin time do not correct to normal range, the presence of ADA and cross-reacting prothrombin/thrombin antibodies will be presumed, and will be directly assessed before a dose escalation decision.

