#### **10.4.1.4 Dose Escalation and Stopping Rules**

Dose escalation to the next dose level (i.e., next cohort) will not take place until after the PI has reviewed the safety data. If any findings in the safety data are of concern, then the SRC comprised of but not limited to, the Sponsor, medical monitor, and the PI will convene to determine if adequate safety and tolerability from the previous cohort has been demonstrated to permit proceeding to the next cohort. The SRC review of all pertinent blinded safety/tolerability data must comprise of physical examinations, ECGs, vital signs, clinical laboratory tests [including coagulation], thrombin time, injection site reaction, and AEs available for all subjects who have completed up to Day 14 procedures.

Data from all subjects in the cohort will be used and reviewed for a dose escalation decision and a minimum of 4 subjects must complete the study (up to Day 14) before proceeding to the next higher dosing cohort.

Together they will make one of the following determinations:

1. To continue with the study as planned.
2. To continue with the study and add additional safety evaluations.
3. To continue with the study and repeat a cohort.

4. To continue with the study by adjusting to an intermediate dose between the current dose and the previous lower dose (i.e., add an additional cohort) or to repeat a cohort, if:
  - a. At least 1 subject has a SAE or visit to the emergency room deemed to be possibly study drug related (see [Section 11.1.8.4](#)).
  - b. At least 25% of subjects in a cohort experience a grade  $\geq 2$  AE deemed to be possibly related to the study drug.
5. To stop the study. The study will be terminated if the following number of subjects meet any of the following criteria and the subjects were determined to have received active drug after unblinding:
  - I.  $\geq 1$  subject that receive drug in a cohort experience:
    - a. Life-threatening hypersensitivity reactions (e.g., anaphylaxis, respiratory symptoms, hypotension etc.).
    - b. Any grade thromboembolic event possibly related to the study drug.
    - c. Any grade bleeding possibly related to the study drug.
    - d. Presence of antibodies against human thrombin or prothrombin.
    - e. Presence of ADA.
  - II.  $\geq 2$  subjects that receive drug in a cohort:
    - a. Has a drug possibly or probably related SAE (see [Section 11.1.8.4](#)).
    - b. Experiences a drug related grade  $\geq 3$  toxicity (see [Section 11.1.8.3](#)).

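### The study must stop for one active subject with any ADA or anti-thrombin/prothrombin antibody, but samples from subjects with normal clotting are not assayed until after Cohort 4

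*Protocol*

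**What the plan says.** **The stop.** Protocol section 10.4.1.4, item 5.I, terminates the study when a single subject found on unblinding to be on active drug meets any listed criterion. Criterion (d) is antibody to human thrombin or prothrombin. Criterion (e) reads, in full, "Presence of ADA". Neither carries a titre, neutralizing or clotting condition. Section 1 records that both were added in Amendment 2 following FDA recommendations.

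**The assay.** Blood for both antibody assays (E-WE thrombin and wild-type thrombin) is drawn at check-in, Day 14 and Day 28. Section 11.1.7.1 sets the timing: "Samples will be shipped to the analytical laboratory for analysis at the end of the study, unless ADA or cross reacting antibodies are suspected". The exception is limited to antibodies "suspected from thrombin time elevation at Day 14 or Day 28". Section 10.2.5 puts the end of the study after the Cohort 4 evaluations, unless dose-limiting safety endpoints come first.

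**The bridge between them.** Section 10.4.1.2 explains the purpose of the clotting tests: "Thrombin time and aPTT at Day 14 will be tested to evaluate whether or not subjects may be generating neutralizing antibodies to thrombin/prothrombin". If clotting stays abnormal on retest and does not correct on mixing, the Synopsis says that ADA and "cross-reacting prothrombin/thrombin antibodies will be presumed, and will be directly assessed before dose escalation decision". Section 10.4.1.4 postpones escalation for ADA data in that case. Otherwise section 10.4.1.2 applies: "If the thrombin time and aPTTs are normal, the next cohort may be dosed if the rest of the safety data is deemed acceptable".

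**The concern.** The stopping rule acts on antibody presence, but the schedule looks for antibodies only when clotting is disturbed. A subject with antibodies and normal aPTT and thrombin time satisfies 5.I.e, and 5.I.d if the antibody binds human thrombin or prothrombin. Nobody will know until the last cohort is finished. At stake is a one-subject mandatory stop in healthy volunteers who have no direct benefit from the drug. For this class of antibody it cannot act before higher doses are given, although the sample that would trigger it has already been taken.

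**Working it through.** The plan states no error rate or operating characteristic for this rule, so there is no figure to reproduce beyond the planned size: 6 + 5 + 5 + 5 = 21 subjects, with 4 × 4 = 16 active and 2 + 1 + 1 + 1 = 5 placebo. The check is mainly a comparison of texts.

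**Step 1. Follow an antibody-positive active subject through the Day 14 tests.**

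| Day 14 finding | What the plan prescribes | Can 5.I.d-e act before escalation? |
|---|---|---|
| Clotting raised, still raised on retest, not corrected on mixing | Antibodies presumed and assayed; escalation postponed | Yes |
| Thrombin time raised, corrects on mixing | Early release of samples (11.1.7.1), but escalation is not tied to the result | Possibly |
| Only aPTT raised, corrects on mixing | 11.1.7.1 names thrombin time only; no early release stated | Arguably not |
| Both normal | Escalation allowed if other safety data are acceptable; sample held | No |

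**Step 2. Look for other text that closes the last row.**

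- Flow chart footnote l says "Immunogenicity testing for ADA will be first performed on blood samples taken on Days 14 and 28", with the check-in sample tested only if those are positive. Section 10.1 is similar. Both give the order in which samples are tested, not a calendar time.
- Section 10.4.1.4 lists the data for escalation review: "The SRC review of all pertinent blinded safety/tolerability data must comprise of physical examinations, ECGs, vital signs, clinical laboratory tests", then thrombin time, injection site reaction and AEs. Immunogenicity is not named. SAP section 4.2 repeats the list without it.
- Section 11.1 lets the investigator or sponsor add tests, and option 2 in section 10.4.1.4 lets the committee add safety evaluations. Both are discretionary, and the committee meets only if there are findings of concern.

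None of these schedules an antibody assay before escalation when clotting is normal.

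**Step 3. Count who could be dosed afterwards.** Inputs are the planned cohorts of 5 (4 active, 1 placebo) for Cohorts 2 to 4, with no replacements or added cohorts.

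| Clotting-normal positive in | Later subjects | Of whom active |
|---|---|---|
| Cohort 1 | 3 × 5 = 15 | 3 × 4 = 12 |
| Cohort 2 | 2 × 5 = 10 | 2 × 4 = 8 |
| Cohort 3 | 1 × 5 = 5 | 1 × 4 = 4 |

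The doses after Cohort 1 are 1.0/0.5 = 2, 2.0/0.5 = 4 and 4.0/0.5 = 8 times the starting dose. If the positive subject is the active sentinel, the other 4 subjects of Cohort 1 (3 active) are also dosed before the assay.

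**Step 4. Place it on a calendar.** Take the minimum intervals, same-day review, and Day d = dosing day + d − 1. The sentinels are dosed on day 1 and the other Cohort 1 groups on days 29 and 43. The last Cohort 1 Day 14 visit is 43 + 13 = day 56, the earliest start of Cohort 2. Repeating the pattern gives Cohort 2 on days 56 and 70, Cohort 3 on 83 and 97, and Cohort 4 on 110 and 124. The last Day 28 visit is 124 + 27 = day 151. A sentinel sample drawn on day 14 would therefore wait at least 151 − 14 = 137 days before shipment. Any real review time lengthens this.

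**The case against.** The strongest reply is that the clotting screen is a deliberate first step. The Synopsis says the Day 14 tests are there to rule out early cross-reacting antibodies, and section 10.4.1.4 carries the chain through to a stop if an assay is confirmed positive. That stands: antibodies that disturb clotting, and do not correct on mixing, are sought before escalation. A reader might infer that the antibody stop can never work in time. The documents do not support that; the gap concerns antibodies that leave clotting normal, and arguably some that correct on mixing.

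Second, immunogenicity is listed among safety assessments in the Synopsis and in sections 10.1 and 11.1, so the remaining safety data in section 10.4.1.2 might be read to include it. Under section 11.1.7.1, however, no result would exist at that point. Separate shipment instructions are also promised and are not available here; they might ship samples sooner, but the protocol's own default is the end of the study.

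Third, the evidence that the plan expects non-neutralizing ADA is limited. SAP Table 11-3 has separate rows for confirmed and neutralizing positives, but it is a mock shell. The point does not depend on it, because 5.I.e applies to any ADA.

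Fourth, harm is not shown. Each subject receives one dose, so no positive subject is re-exposed, and 3 of the 15 later subjects receive placebo. A reader might infer a probability of dosing past the stop, or a known hazard. Neither can be drawn from the documents.

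**Conclusion.** The concern holds for antibodies with normal clotting. The stop is unconditional, the only prespecified route to an antibody result before the end of the study is a clotting abnormality, and escalation may proceed without that result. The size is a count of exposure: up to 15 further subjects, 12 active, after such a positive in Cohort 1. It assumes the planned 21 subjects, escalation through Cohort 4, and no discretionary early assay. It should be fixed because a mandatory safety rule and its measurement schedule disagree. No estimate of the resulting risk is available.

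**What to change.** In section 11.1.7.1, ship and assay the samples already collected cohort by cohort, with the check-in sample if a later one is positive. Require the sentinels' Day 14 and Day 28 results before the rest of Cohort 1 is dosed. Require all available ADA results, and at least every Day 14 sample, before each escalation. Add ADA to the data list in section 10.4.1.4, and state that a confirmed positive in an active subject halts dosing.

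The cost is protocol wording, a few more shipments and assay runs, and about one assay turnaround at each of four points (the sentinel review and three escalations). No extra blood or subjects are needed. Turnaround is not given. If it were 1 to 2 weeks (an assumption), the added time would be at most about 4 × 1 = 4 to 4 × 2 = 8 weeks, less any overlap with safety review.

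Some exposure remains. A cohort's second group may be dosed the day after the first group's Day 14 draw, and an antibody first seen at Day 28 may appear after escalation. The protocol should say whether this is accepted.

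If the sponsor regards the clotting and mixing screen as sufficient, the alternative is to limit 5.I.d-e to antibodies found through that pathway. This costs only wording, but narrows a stop that was added following FDA recommendations.

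Two minor clarifications are separate: use one aPTT and/or thrombin time trigger throughout, and name confirmation of a stopping criterion among the permitted code breaks in section 10.4.4.2.
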